5.2.3 ASSESSMENTS DURING FOOD CHALLENGES

The baseline food challenges are termed 'high-risk' on the basis that we expect the challenges to be positive. To minimize risk to the patient, all challenges will take place on a Paediatric Allergy Research Unit (PRU) where food challenges are performed on a regular basis, and staff are familiar with the management of allergic reactions including anaphylaxis through clinical experience and regular training. Since many of the study participants will be new to the research team, we propose additional safety precautions at the initial baseline challenge:

i. Intravenous access: Cannulation will be performed in order to secure intravenous access. This will allow treatment to be easily and rapidly administered in the event of a significant allergic reaction. In order to minimize discomfort to the child, we will offer local anaesthetic cream to be applied at least 30 minutes prior to cannulation, according to local practice.

Blood will be collected prior to, during and after challenge via the cannula, in order to confirm a clinical reaction using objective laboratory assessments. This procedure will not cause discomfort to the child, as the cannula will already be in situ. Where the cannula does not bleed back, no further venepuncture will be attempted. If cannulation is not possible (for whatever reason), the challenge may proceed if authorised by the Chief Investigator, on the basis that emergency medicines can also be given by the intramuscular route.

At the challenge visit, a maximum total volume of 2.5ml/kg (max 75ml) blood (up to 40ml prior to starting the challenge) will be collected for baseline laboratory assessments of immunological function relating to peanut allergy and assessment of tolerance (see section 5.7.2). These tests will include IgE antibodies to peanut (including peanut components); inflammatory mediators; inflammatory cell activation (by flow cytometry); and storage of RNA (using the PAXgene system) and DNA for latter analysis of protein signal transcription. We have elected to perform this test at this initial challenge, rather than at the screening visit, in order to reduce the number of blood tests required.

- ii. **Non-invasive monitoring**: Children will be monitored during food challenges, using non-invasive monitoring. In addition to standard measurements of heart rate, blood pressure and oxygen saturations, we propose additional non-invasive measurements in order to gain as much information as possible about allergic reactions under controlled conditions, as follows:
 - a. **Central blood pressure**: In addition to peripheral (brachial) BP, central BP will be measured using the Pulsecor BPplus non-invasive CardioScope II monitor (CE-marked) (Figure 4). Use is similar to a conventional BP cuff/monitor with measurements obtained within 60 seconds, and is very well tolerated by children.
 - Rationale: The difference between central and peripheral systolic BP may be more representative of the effect of vasodilatation during a food allergic reaction. Furthermore, central diastolic BP correlates better with coronary perfusion than peripheral diastolic BP. There may be a difference between the ability of individuals to maintain central BP during a systemic allergic reaction, which could relate to the clinical symptoms observed.

Figure 4: Pulsecor II Central Blood Pressure monitor.

b. Non-invasive hemodynamic monitoring: In older children (above 12 years), continuous data will be obtained using non-invasive hemodynamic monitoring (Cheetah NICOM monitor); this type of monitoring is not validated in younger children, nor is practical due to the need to be inactive during measurements. The NICOM monitor has been extensively validated, has FDA approval and is CE marked. Data is collected through 4 ECG-type sensors (size 108 x 20 mm) placed on the front or back of the thorax, as shown in Figure 5. Measurements are not prone to movement artefact. The monitor allows for continuous cardiovascular monitoring (including cardiac output and peripheral resistance) during challenges.

Rationale: It is unknown as to how cardiac output varies during an allergic reaction. Some individuals may be able to compensate for capillary bed vasodilatation during a systemic allergic reaction by modulating cardiac output. The assessment of cardiac output will also facilitate the estimation of peripheral vasodilatation through measurement of total peripheral resistance.

[figure not shown]

Figure 5: NICOM Sensor placement

To provide further validation of the measurements taken by the NICOM monitor, during some challenges participants will also be invited to undergo intermittent cardiac echocardiography (performed by a trained healthcare professional according to standard protocols in use at our hospital).

5.2.4 MANAGEMENT OF SYMPTOMS DURING PEANUT EXPOSURE

Any allergic reaction happening during the observation period following dose administration will be managed according to the British Society for Allergy and Clinical Immunology (BSACI) Allergy Action Plans for children (Figure 6).

[figure not shown]
Mild-moderate (non-anaphylactic) symptoms (as defined in Figure 6) will be treated with cetirizine as per local policy. Symptoms of anaphylaxis will be treated initially with IM adrenaline. Where feasible, the child or parent will use their adrenaline auto-injector device to administer the (first) dose of adrenaline in this event, as this can increase compliance with the Plan's recommendations outside the home environment and reduce anxiety relating to the use of auto-injector devices.

Allergy Action Plan

Clinic details

THIS CHILD HAS THE FOLLOWING ALLERGIES:

How to give EpiPen®

Form fist around EpiPen® and PULL OFF BLUE SAFETY CAP

SWING AND PUSH ORANGE TIP against outer thigh (with or without clothing) until a click is heard

HOLD FIRMLY in place for 10 second

REMOVE EpiPen®. Massage injection site for 10 seconds

Keep your EpiPen device(s) at room temperature, do not refrigerate.

For more information and to register for a free reminder alert service, go to www.epipen.co.uk

Patient support groups:

http://www.allergyuk.org or www.anaphylaxis.org.uk ©The British Society for Allergy & Clinical Immunology www.bsaci.org

Mild-moderate allergic reaction:

- · Swollen lips, face or eyes
- Itchy / tingling mouth
- Abdominal pain or vomiting
- Hives or itchy skin rash
- Sudden change in behaviour

ACTION:

- · Stay with the child, call for help if necessary
- · Give antihistamine:
- · Contact parent/carer

(if vomited, can repeat dose)

Watch for signs of ANAPHYLAXIS (life-threatening allergic reaction):

AIRWAY: Persistent cough, hoarse voice,

difficulty swallowing, swollen tongue

Breathing: Difficult or noisy breathing,

wheeze or persistent cough

Consciousness: Persistent dizziness / Pale or floppy

Suddenly sleepy, collapse, unconscious

If ANY ONE of these signs are present:

- 1. Lie child flat. If breathing is difficult, allow to sit
- 2. Give EpiPen® or EpiPen® Junior
- 3. Dial 999 for an ambulance* and say ANAPHYLAXIS ("ANA-FIL-AX-IS")

If in doubt, give EpiPen®

After giving Epipen:

- 1. Stay with child, contact parent/carer
- 2. Commence CPR if there are no signs of life
- If no improvement after 5 minutes, give a further EpiPen[®] or alternative adrenaline autoinjector device, if available

*You can dial 999 from any phone, even if there is no credit left on a mobile. Medical observation in hospital is recommended after anaphylaxis.

Additional instructions:					
This is a seedinal decompositation on sub-leasurement	d by the continue to a time to				
altered without their permission.	ed by the patient's treating health professional and cannot be				
This plan has been prepared by:					
Hospital/Clinic:					

Figure 6: BSACI Allergy Management Plan

5.3 TOLERANCE CHECK, RANDOMISATION AND WP1: ORAL IMMUNOTHERAPY

Eligible participants (who have a positive DBPCFC, confirming IgE-mediated peanut allergy) will then undergo a one-shot food challenge to confirm tolerance to at least ¼ boiled peanut to confirm eligibility. Children able to tolerate boiled peanut will then be randomized to either active treatment (OIT) or control, on a 2:1 basis.

Randomisation needs to occur after tolerance to ¼ boiled peanut has been demonstrated, and updosing commenced immediately on safety grounds. Were randomisation (and thus further daily dosing) to be delayed, there would be potential for priming which might result in subsequent reactivity to a previously tolerated dose of boiled peanut. Immediate randomisation and updosing thus ensures safety.

5.3.1 TOLERANCE CHALLENGE TO BOILED PEANUT

All children will undergo a single-dose OPEN (unblinded) food challenge to determine the starting dose of boiled peanut. Tolerance to at least ¼ boiled peanut is an eligibility criterion, and must be demonstrated prior to randomisation in all children. The open, single dose challenge will involve the consumption of ¼ boiled peanut (boiled for 4 hours) followed by a 2 hour observation period. The criteria listed in Section 5.2.2 will be used to determine outcome of this food challenge.

Children who are unable to tolerate ¼ boiled peanut will not be eligible for the study, and will be transferred back to routine clinical care.

5.3.2 RANDOMISATION

Once tolerance to ¼ boiled peanut has been demonstrated, the participant will be randomised using an online randomization tool (www.sealedenvelelope.com). Randomisation will be blocked (using random permuted blocks) to ensure that the groups are balanced, and include a level of stratification according to whether the child is predominantly sensitized to a specific peanut protein components (Ara h 2). Pilot data indicates that the boiling process affects Ara h 2 content more than other peanut proteins. Thus, patients who are predominantly sensitized to Ara h 2 may be more likely to have a successful outcome than those allergic to other peanut proteins.

The Ara h 2 predominant Phenotype is defined as:

- Specific IgE to Ara h 2 > 1.0 kUA/l
- Specific IgE to Ara h 1 and Ara h 3 <1.0 kUA/l

5.3.3 CONTROL GROUP

Subjects randomized to the control group will receive current standard care according to best practice (as per British Society for Allergy and Clinical Immunology guidance). This includes:

- A food allergy management plan (Figure 5), with provision of rescue medication including an adrenaline autoinjector device. Families and participants will be instructed in the prompt recognition and treatment of allergic reactions.
- **Contact information** for the team, which will include telephone contact number for the team and an email address which will be checked daily by the research team from Monday to Friday for non-urgent queries.
- **Dietary advice on peanut avoidance**. Participants will not be allowed to ingest peanut for the whole study duration (52 weeks).
- A home diary sheet, on which parents will log all accidental reactions experienced. Participants will also be
 offered an opportunity to 'opt-in' to using an electronic 'mobile app' diary in parallel to the paper-based diary.

Children (and their parents) will undergo quality-of-life assessments at 0, 3, 6 and 12 months (see 5.7.1).

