5.1 RECRUITMENT AND SCREENING VISITS

Peanut-allergic children will be recruited through our clinical service at St Mary's Hospital (Imperial College Healthcare NHS Trust), one of the largest tertiary services in Europe providing specialist paediatric allergy services to the North Thames Region. We will also recruit through our local paediatric allergy network in North West London, including the use of PIC sites at the larger allergy centres. This study requires frequent visits (once every 2-4 weeks) to the Research Unit, thus it is important that participants live relatively local to the unit to minimize travel time and impact on other daily activities.

Potential participants will receive the Study Information either in person, by post or via email, following which the participants will be screened by telephone conversation with their parents, to determine likelihood of true peanut allergy and thus suitability for this study. Suitable participants will then have an appointment made for a screening visit.

The following will take place at the first screening visit:

- Informed consent
- Clinical history and physical examination
- Skin prick test (SPT) to commercial crude peanut extract and boiled peanut slurry according to national guidelines
- For children with asthma, current asthma status will be assessed by the clinician, with the help of lung function testing and completion of a validated asthma control test
- For children with eczema, eczema will be assessed using the SCORAD system¹¹ (which provides an objective measure of eczema severity) as well as completion of a POEM questionnaire, a validated patient-based symptom measure questionnaire

The first screening visit may take place on the same day as the first baseline food challenge, if requested by the family.

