- **Contact information** for the team, which will includes a dedicated mobile phone number with 24/7 access to a senior member of the medical team for urgent queries, and an email address which will be checked daily by the research team from Monday to Friday for non-urgent queries.
- **Dietary advice on peanut avoidance**. Participants receiving OIT will not be allowed to ingest peanut for the whole study duration (52 weeks) excluding the OIT doses.
- A home diary and instruction sheet, which will specify to parents what dose to give their child, and on to which they will log all doses taken at home and any resulting adverse events. Subjects will be asked to record any symptoms, duration, timing in relation to OIT dose and any exacerbating factors (e.g. exercise, excessive tiredness, viral illness). In the event of any symptoms, the family needs to contact the research team for advice. Participants will also be offered an opportunity to 'opt-in' to using an electronic 'mobile app' diary in parallel to the paper-based diary, the aim being to facilitate reporting by study participants and validate this approach for future OIT studies.

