5.3.4.1 UPDOSING

At each step (i.e. all dose increases), the dose will first be given under medical supervision on the Research Unit, followed by observation for at least one hour (2 hours if participant has previously experienced a delayed reaction). Prior to a dose increase, the supervising clinician will assess the participant to ensure:

- No significant allergic reactions to doses given in previous 2 weeks.
- No acute exacerbation of asthma in the past week.
- No concurrent systemic illness.

The dose can be mixed into a carrier (such as low fat (rather than full fat) yoghurt, for example) if desired. Children will be monitored under medical supervision for one hour following dose administration. Following each dose increase, that dose will be given to participants at home daily for a minimum of 2 weeks until the next increase is performed.

STEP	PEANUT Boiling time	No. of peanuts / day	No. weeks at this dose (minimum)	Cumulative No. of weeks (minimum)	Approximate Peanut protein (mg)
pre-A	4 hours	1/8	2	-	15
pre-B	4 hours	1/4	2	-	30
1	4 hours	1/2	2	2	65
2	4 hours	1	2	4	130
3	4 hours	2	2	6	260
4	4 hours	4	2	8	520
5	4 hours	8	2	10	1040
6	2 hours	4*	2	12	520
7	2 hours	8	2	14	1040
8	1 hour	2*	2	16	260
9	1 hour	4	2	18	520
10	1 hour	8	2	20	1040
11	1/2 hour	4*	2	22	520
12	1/2 hour	8	4	26	1040
	Open OFC to	roasted peanut (t	o determine if u	pdosing can be co	onverted to roasted):
		_	=	•	anuts up to Wk 52
	• If tole	erates 300mg dose	e, continue updo	osing as follows:	
13	n/a	½ roasted PN	4	30	125
14	n/a	1 roasted PN	4	34	250
15	n/a	2 roasted PN	4	38	500
16	n/a	4 roasted PN	4	42	1000

Table 1: Updosing protocol for Peanut (PN) OIT using boiled and then roasted peanut.

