7.2.2 ANALYSIS OF SECONDARY ENDPOINTS

The following secondary analyses will be performed, using two-sided testing for non-parametric data at a p<0.05 level of significance:

- Relative change in clinical threshold (NOAEL, LOAEL) to roasted peanut at 6 and 12 months in active vs control, using Mann-Whitney U test.
- Proportion of subjects who tolerate 1.4g (or more) roasted peanut protein in the active and control groups, 12 months after randomization and following cessation of all peanut intake for 4 weeks after 1 and 3 years of OIT, using a two-sided Fisher's exact test at a p<0.05 level of significance.
- Change in quality of life assessments before, and at 6 and 12 months after OIT, as assessed by FAQL-Questionnaire in children, teenagers and their parents in the active vs control groups using paired and group comparisons by non-parametric testing.
- The incidence of adverse events experienced between active and control groups. Statistical differences will be
 determined using Fisher's exact test for proportions or using non-parametric tests for graded reactions.
 Logistic regression will be used to assess the influence of age, gender, asthma status and prior history of
 anaphylaxis on incidence of adverse events.
- Immunological outcome measures pre-, during and post- 12 months of OIT, using Mann-Whitney U test (for paired comparisons) or Friedman's test (for trends over time).

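### The between-arm test of all adverse events is open to ascertainment bias against OIT, because the year-1 diaries and contact schedules differ by arm and no common elicitation is set

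*Combined protocol and SAP*

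**What the plan says.** Four parts of the plan bear on this.

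- **Control arm, section 5.3.3.** Families receive "A home diary sheet, on which parents will log all accidental reactions experienced". Scheduled contact is light: "Children (and their parents) will undergo quality-of-life assessments at 0, 3, 6 and 12 months", and section 5.4 adds the 12-month blinded challenge.
- **OIT arm, sections 5.3.4 and 5.3.4.1.** The diary covers doses and the events that follow them, and "Subjects will be asked to record any symptoms, duration, timing in relation to OIT dose and any exacerbating factors". There is also a duty to report: "In the event of any symptoms, the family needs to contact the research team for advice". Section 5.3.4.3 extends this to intercurrent illness that is not linked in time to a dose. On visits, "At each step (i.e. all dose increases), the dose will first be given under medical supervision on the Research Unit". The clinician first checks for recent allergic reactions to doses, asthma exacerbation and systemic illness.
- **Both arms, section 6.2.** All adverse events go on the CRF from consent onward, whatever their severity or cause. They may come to light by observation, by questioning or through an unprompted complaint. No timetable for questioning is given.
- **Analysis, section 7.2.2.** The comparison is "The incidence of adverse events experienced between active and control groups", with differences "determined using Fisher's exact test for proportions or using non-parametric tests for graded reactions". It is not restricted to allergic events. Section 6.1 defines an adverse event to include events unrelated to the intervention.

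**The concern.** A test of incidence between arms assumes that an event of a given kind has the same chance of reaching the record in either arm. Here, one arm is asked about any symptom, told to ring in, and checked at every dose increase. The other is asked in writing about accidental reactions and has few scheduled contacts. The trial is open label, so blinding offers no protection.

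Children with asthma, rhinitis or eczema may enrol (section 4.2). Wheeze, nasal symptoms and abdominal pain will therefore occur in both arms for reasons unrelated to peanut. If these are written down more completely in the OIT arm, part of any excess reported for OIT is detection. Section 3.2 gives the safety comparison as one reason for having a control group. The logistic regression in the same item of section 7.2.2 would carry the same problem if both arms were pooled in it.

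**Working it through.** **Step 1: set the two arms side by side (year 1).**

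| | OIT | Control |
|---|---|---|
| Diary content | Doses, resulting events, any symptoms | Accidental reactions |
| Duty to contact the team | For any symptom | None stated |
| Scheduled contact after randomisation | A visit at each dose increase, plus an open challenge and QoL | QoL at 3, 6 and 12 months; 12-month challenge |
| Questions on recent health | Before each increase | None scheduled |

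Table 1 in section 5.3.4.1 has 16 numbered steps and two preliminary ones, 16 + 2 = 18 at most. For a child who starts at step 1 and takes every step, steps 1 to 11 take 11 × 2 = 22 weeks, step 12 takes 4, and steps 13 to 16 take 4 × 4 = 16. The total is 42 weeks at the earliest. No visit interval is given after that.

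**Step 2: ask whether another section closes the gap.** Section 6.2 makes recording universal. But each route it names for discovering an event depends on contact or on a family volunteering information, and those are what differ. It narrows the gap without closing it.

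**Step 3: ask which events are affected.** Controls are told to avoid peanut, so any peanut reaction outside a challenge is accidental and belongs in their diary. The gap therefore lies mainly in background and non-peanut symptoms, and so in the total count of adverse events.

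**Step 4: illustrate the size.** The plan gives no adverse-event rate, capture rate or power for this comparison, so there is no stated figure to reproduce. The group sizes, 30 and 16, come from section 7.1; the test and 0.05 level come from section 7.2.2. The rest is assumed: true incidence π is equal in both arms, capture in OIT is complete, and a control child who has an event is recorded with probability c.

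Recorded events are then X ~ Binomial(30, π) in OIT and Y ~ Binomial(16, cπ) in controls. The false-positive rate is the sum of P(X = x)P(Y = y) over all pairs (x, y) for which the two-sided Fisher p-value is below 0.05.

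| True incidence π | c = 1 | c = 0.875 | c = 0.75 | c = 0.5 |
|---|---|---|---|---|
| 30% | 3.7% | 4.0% | 5.5% | 13.6% |
| 50% | 3.1% | 4.4% | 8.9% | 31.0% |
| 80% | 3.4% | 10.9% | 28.4% | 75.4% |

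At π = 50% the expected record is 15 of 30 in OIT against 8, 7, 6 and 4 of 16 in controls across the four columns. The excess rejections run almost wholly against OIT. With 24 v 13 children (the planned numbers after 20% loss), π = 50% and c = 0.5 give 24.1%.

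**Step 5: note what c means.** Fisher's test on proportions counts children with at least one event, so c is capture per child. If an affected child has three independent events, each recorded with probability 0.5, then c = 1 − 0.5³ = 0.875. Poor capture of single events can thus leave per-child capture high, which points to the milder columns.

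**The case against.** The strongest reply is that the safety outcome in section 3.1.2 is defined by allergic symptoms, and that section 3.2 describes the control comparison in terms of accidental allergic reactions. The control diary asks for exactly those. This stands for peanut reactions and narrows the point considerably. It does not answer section 7.2.2, whose wording covers all adverse events.

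A second reply is that the OIT diary can be read as a dose-reaction diary, and that the pre-dose checks cover three fitness items and are not open questioning. That is fair, and it means that fuller recording of background symptoms is an inference. Even so, two of the three items are background illness, section 5.3.4.3 asks for calls about illness unrelated to dosing, and controls have no counterpart to either.

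Third, more contact is inherent to OIT. That also stands, but a narrower control diary is not inherent.

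Three stronger readings are tempting, and the documents do not support them. A reader might infer that controls record nothing but accidental reactions; section 6.2 applies to both arms, so the diary is not the sole source. A reader might infer that OIT children are seen at a fixed short interval all year from "This study requires frequent visits (once every 2-4 weeks) to the Research Unit"; that is a general statement in section 5.1, and the updosing schedule supports it only to about week 42. And a reader might infer that an excess of events under OIT would be an artefact; section 1.1 describes frequent reactions with roasted-peanut OIT, so much of any excess could well be real.

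**Conclusion.** The point holds in a limited form. The section 7.2.2 comparison of all adverse events is open to ascertainment bias against OIT, of unknown size, chiefly for background and non-peanut symptoms. Within the illustration the effect runs from negligible (false-positive rate about 4% with 87.5% per-child capture and incidence of 30% or 50%) to serious (31% with half capture and 50% incidence). Those figures rest on assumed incidence and capture and on equal true incidence, which is itself unlikely here. They show that the test is sensitive to unequal capture; they do not estimate the bias in this trial. The primary endpoint comes from a blinded challenge offered to both arms at 12 months and does not depend on the diaries. This is a minor point with a cheap remedy.

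**What to change.** 1. For months 0 to 12, give control families the same symptom diary as OIT families, without the dose fields.
2. State in section 7.2.2 that the formal between-arm test covers allergic reactions and adrenaline use outside food challenges, and serious events meeting the general criteria in section 6.1. Challenges are set aside because the OIT arm has extra open ones (sections 5.3.4 and 5.3.4.2).
3. For that test, leave out the separate rule in section 6.1 that classes treated symptoms after an OIT dose as serious. Controls take no OIT doses in year 1, so the rule can apply to one arm only. Such events would still be reported for the OIT arm.
4. Describe all other adverse events by arm without a test, and say that contact differed.

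The cost is a change to one form, a few lines in the analysis section, a slightly heavier diary for controls, and CRF entry, grading and attribution of the additional control events. No extra visits are needed. Where year-1 diaries have already been collected, the change to section 7.2.2 still helps on its own.
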